Assessment of neuromuscular activation of the diaphragm. Neuromuscular activation of the diaphragm will be assessed by recording diaphragm EMGs from the surgically-implanted intramuscular stimulating electrodes.^{11,75} This approach will allow for comparisons of EMG recordings across time and reduces the methodological limitations associated with surface or percutaneous EMG approaches.⁹ EMGs will be recorded during non-stimulated respiration (diaphragm pacer turned off) and simultaneously with assessments of respiratory function. These assessments may include maximal inspiratory pressures and assessments of resting tidal breathing and measurement of flow volumes using standard spirometry.^{76,77}

Primary outcomes to characterize neuromuscular activation of the diaphragm and assess changes in diaphragm activation associated with intramuscular diaphragm stimulation will include: amplitude and timing characteristics (raw, filtered EMGs and normalized);^{76,77} neural respiratory drive to evaluate diaphragm muscle activation during tidal breathing relative to activation capacity during maximal inspiratory maneuvers;^{77,78} and time-frequency characteristics of the diaphragm EMGs (wavelet analysis).^{75,79-81} Methods pertaining to diaphragm EMG signal acquisition and processing are explained below.

Diaphragm EMG acquisition and signal processing. The PI has extensive experience with EMG acquisition and analyses in humans.^{69,70} EMGs will be recorded from the externalized pacing wires which connected to each of four intramuscular electrodes (2 in each hemidiaphragm). The implanted, remote sub-cutaneous electrode will serve as the ground.¹¹ A custom-connector (Synapse Biomedical, Oberlin, OH) will be used to link the exposed pacing wires to our EMG acquisition system. EMG signals will be amplified and band pass filtered (10 Hz to 1000 Hz), acquired at a sampling frequency of 2 kHz, and saved to a computer for off-line analysis.

To acquire the diaphragm EMG signals, the pacer will be shut off to allow connection to the EMG acquisition system. It is feasible to shut off the diaphragm pacer for several reasons.

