First, most of the individuals with SCI have residual respiratory control and are able to maintain sufficient respiration for a short time period. It is part of standard procedures to turn off the pacer on a regular basis to change the pacer batteries. Consistent with this process (turning off the pacer when changing the batteries), supplementary respiratory support will be provided as needed (i.e. mechanical ventilation) and oxygen saturation will be monitored at all times to ensure adequate respiration (>90% O₂ saturation) during the assessments. Second, all assessments will be overseen by the participant's clinical medical team (ICU) with oversight from the participant's physician. All assessments will include cardiorespiratory monitoring. Finally, an assessment will be halted at any time the patient indicates distress or indicates that he or she would like to stop the assessment. In this case, the pacer will be re-connected and turned on and respiratory support will continue until the patient is comfortable.

Neuromuscular activation outcomes. Raw, filtered EMGs, as well as normalized signals will be assessed for timing and amplitude characteristics. Normalization will be based on maximal amplitude of the signals recorded during tests of maximal inspiratory pressure and sniff nasal inspiratory pressure.^{76,78,89} Signals will be full-wave rectification and amplitudes calculated based on the root mean square or integral of the signal. Comparisons of normalized signal amplitudes, burst timing, and burst durations will provide evidence of changes in neuromuscular activation of the diaphragm in association with intramuscular stimulation of the diaphragm and following C-CSI. Increased EMG amplitudes are indicative of greater motor unit recruitment and suggest gains in muscle force generation.^{65,75,90}

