To determine the relationship between diaphragm muscle activation during resting tidal breathing and diaphragm activation capacity during maximal inspiratory maneuvers, the relative level of "neural respiratory drive" will be calculated from the normalized diaphragm EMGs. Neural respiratory drive is a measurement approach used to quantify the respiratory load/capacity relationship and is a marker of respiratory disease severity.^{78,89,91,92} Changes in neural respiratory drive are associated with changes in respiratory function and breathlessness during exercise in patient populations.^{78,92} Neural respiratory drive will be calculated based on the root mean square of the diaphragm EMG signals during resting tidal breathing normalized to the maximal EMG values obtained during the maximal inspiratory maneuvers.⁸⁹

Finally, time-frequency characteristics of diaphragm EMGs will be assessed using wavelet analysis.^{75,80,93} Continuous wavelet analysis using a Morlet wavelet will be used to decompose the diaphragm EMG signals into individual frequency components as a function of time. The Morlet wavelet will be used because it provides a reasonable balance between time and frequency localization.⁹⁴ Wavelet transforms of the EMG signals will be calculated using a base algorithm in Matlab (The Mathworks, Natick MA) developed by Torrence and Compo and available at URL: <http://paos.colorado.edu/research/wavelets>.⁹⁵ Comparisons of the frequency characteristics of the EMGs recorded during different respiratory maneuvers and longitudinally will provide novel insight regarding motor unit recruitment, firing frequencies, muscle fiber changes, as well as central activation of phrenic motor neurons.^{75,80,81}

Higher frequencies of the EMG suggest greater recruitment of larger muscle fibers and faster conduction velocities. For instance, a shift toward higher frequencies during more forceful maneuvers or over-time would suggest recruitment of larger, more forceful motor units with higher recruitment thresholds.^{96,97} Such changes would support our previous observations^{8,23} and others^{11,36} that intramuscular stimulation promotes neural and muscular adaptations.

Assessments of diaphragm muscle strength and respiratory function.

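### Does leaving the EMG normalization session unnamed spoil normalized amplitude as evidence of changed diaphragm activation?

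*Combined protocol and SAP*

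**What the plan says.** All the relevant text is in section 6, Research Plan, of the combined protocol and SAP.

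- **Assessment of neuromuscular activation of the diaphragm** lists the primary EMG outcomes. They include "amplitude and timing characteristics (raw, filtered EMGs and normalized") and, as a separate item, "neural respiratory drive to evaluate diaphragm muscle activation during tidal breathing relative to activation capacity during maximal inspiratory maneuvers". Wavelet time-frequency measures are a third group. Of recording from the implanted pacing electrodes it says: "This approach will allow for comparisons of EMG recordings across time".
- **Neuromuscular activation outcomes** gives the divisor: "Normalization will be based on maximal amplitude of the signals recorded during tests of maximal inspiratory pressure and sniff nasal inspiratory pressure". The metric is left open, with "amplitudes calculated based on the root mean square or integral of the signal". The stated use is that "Comparisons of normalized signal amplitudes, burst timing, and burst durations will provide evidence of changes in neuromuscular activation of the diaphragm".
- The paragraph on **neural respiratory drive** that follows defines it from the root mean square (RMS) of the signal "during resting tidal breathing normalized to the maximal EMG values obtained during the maximal inspiratory maneuvers", and describes its meaning: "Neural respiratory drive is a measurement approach used to quantify the respiratory load/capacity relationship and is a marker of respiratory disease severity".
- **Assessment Overview** places maximal inspiratory pressure tests in every assessment. **Post-tests** repeats the pre-stimulation battery after each stimulation block. **Pre-stimulation Assessment** plans two sets of tests before the stimulator is switched on.

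No section says whether the maximum comes from the session being normalized or from one fixed session.

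**The concern.** A maximum is available at every session, so dividing each session by its own maximum is a natural reading. On that reading three things look wrong.

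1. Normalized tidal amplitude, if measured as RMS, becomes the same quantity as neural respiratory drive, so two outcomes listed separately collapse into one.
2. The normalized maximum is about 100% at every session by construction and carries no information on change.
3. The divisor can itself respond to stimulation. The Research AIM expects pacing to increase activation, and the Assessment Overview treats the maximal test as a measure of maximal activation. A normalized tidal amplitude could then stay level or fall while tidal and maximal activation both rise.

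At stake is a listed primary outcome that could contradict raw amplitude and be read as evidence against the hypothesis. A paired test would not cure this, because the cause is the moving divisor. The plan also gives no favourable direction for neural respiratory drive and no rule for reading a disagreement between raw and normalized results.

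**Working it through.** The plan gives no figure on this point to reproduce, and no EMG gains or variances. Every gain below is an assumption.

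**Notation.** T is tidal EMG amplitude and M is maximal-manoeuvre EMG amplitude, both before stimulation. After stimulation they are aT and bM.

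**Step 1: same-session divisor.** The ratio goes from T/M to aT/(bM), so the relative change is a/b − 1.

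| Tidal gain | Max +0% | Max +10% | Max +20% | Max +30% |
|---|---|---|---|---|
| +10% | +10.0% | 0.0% | −8.3% | −15.4% |
| +20% | +20.0% | +9.1% | 0.0% | −7.7% |
| +30% | +30.0% | +18.2% | +8.3% | 0.0% |

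For example, 1.10/1.30 − 1 = −15.4%. With assumed starting values T = 20 and M = 100, the ratio goes from 20.0% to 22/130 = 16.9%. The arithmetic of the concern is right.

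**Step 2: raw amplitude.** The change is aT/T − 1 = a − 1, which is +10%, +20% or +30% in the three rows, whatever M does. The raw maximum likewise changes by b − 1. Both can be read from the signals the plan already analyses.

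**Step 3: fixed pre-stimulation divisor R.** The change is (aT/R)/(T/R) − 1 = a − 1. R cancels within each participant. On a percentage or log scale, a paired comparison with a fixed divisor is therefore the raw comparison in other units.

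**Step 4: a change in recording gain.** Suppose the post-stimulation recording gain changes by a factor g. The same-session ratio is (g·aT)/(g·bM) = aT/(bM), so g cancels. On the fixed divisor it is g·aT/R, so g stays. With g = 0.9 and a true rise of 10%, the fixed-divisor amplitude reads 0.9 × 1.10 − 1 = −1%. Each choice protects against one distortion and is exposed to the other.

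**Step 5: is normalized tidal amplitude the same as neural respiratory drive?** Only if three conditions hold: RMS is the metric, both divisors use the same manoeuvres, and both use the same reference. The plan allows the integral for amplitude but specifies RMS for drive. It names the sniff test for amplitude but only maximal inspiratory manoeuvres for drive. In a synthetic check with a maximal burst twice as long as the tidal burst, the RMS ratio was 0.206 and the integral ratio 0.104, so the metric alone can separate the two. The identity also does not depend on a same-session divisor; any shared reference produces it.

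**Step 6: outcomes outside the problem.** Burst timing, burst duration and the wavelet frequency measures do not depend on amplitude scaling.

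**The case for a change.** The strongest case for a change is that an outcome called primary should be fully defined before data are seen. The likeliest reading lets it move against the hypothesis when the hypothesis is true, and the repair would be a few lines of text with no burden on participants. The study is also meant to inform a larger trial, so a loose definition could carry forward.

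The omission is real, and so is the algebra. The open choice of metric and the unstated direction of neural respiratory drive are real gaps too. The sniff test appears in the normalization sentence but not in the batteries under Assessment Overview or Diaphragm muscle strength. That looks clerical: if no sniff is recorded, the maximal inspiratory pressure manoeuvre supplies the maximum.

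One further point deserves weight. Raw amplitude is a weak safeguard under the planned unpaired Mann-Whitney test, because spread between participants swamps the change. In one simulation with ten participants, both gains at 30%, a between-participant amplitude CV of 50%, a tidal/maximum ratio CV of 20%, and measurement CVs of 10% (tidal) and 15% (maximal trials), power was 3.5% for raw amplitude and 75.5% for a fixed divisor. All those inputs are assumed. With noisier measurements (CVs 20/20% and 30/30%) the fixed-divisor figure falls to about 42% and 21%. The gap comes from ignoring the pairing, which is a separate question about the test. In the paired simulations the raw and fixed-divisor results coincide, as Step 3 requires. It is no argument for a particular normalization session.

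**Conclusion.** No change to the plan follows. The gap is missing detail together with a fair trade-off.

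- **The harm is conditional.** It needs a same-session divisor, which no section states, and a maximum that rises over blocks of about 1 to 12 hours, for which the documents give no EMG size. Under those assumptions the distortion in the grid runs up to a 15% apparent fall against a true 10% rise. If the maximum does not rise, there is none.
- **The evidence is not lost.** Raw amplitude is a listed primary outcome from the same fixed electrodes, and it changes by the true tidal gain in every cell. A reader who sees raw tidal amplitude rise, raw maximum rise more and the ratio fall has a coherent picture: activation rose and load relative to capacity fell. That is how neural respiratory drive, as the plan describes it, should behave.
- **The alternative gains little.** A fixed divisor reproduces the raw percentage change and gives up the cancellation of recording gain, so reasonable analysts differ on the choice.
- **The open details are routine.** Session, metric, manoeuvre and direction are settled in off-line processing, and can be reported with the results of a ten-person proof-of-concept study.

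This conclusion assumes that raw and normalized amplitudes are reported side by side, as the outcome list implies. It does not rest on the simulated power figures.

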Following diaphragm pacer placement, the pre-stimulation assessment (prior to turning **on** the diaphragm stimulation) will be initiated approximately 18-24 hours after pacer implantation, once the patient is medically stable and able to participate. Waiting 18-24 hours after pacer implantation is standard of practice based on the procedures used by the diaphragm pacing surgical team ([name]). For individuals enrolled within 5-days after pacer implantation, the pre-stimulation assessment will occur as soon as possible after enrollment. The pre-stimulation assessment will include clinical respiratory tests and recording of diaphragm EMGs which are detailed in sections below. Pre-stimulation assessment will take approximately 2 hours to complete. To obtain a clear pre-stimulation assessment, two sets of tests will be conducted, about 1 hour apart. Ample time for rest breaks will be provided. The participant will be closely monitored and testing will be adjusted for each participant's comfort and medical needs.

*Post-tests (following periods of diaphragm stimulation)**

[figure not shown]
Post-testing will occur after 3 different blocks of diaphragm stimulation, and will occur with the stimulator turned off (Figure 3). These blocks are contiguous, meaning block 2 will begin immediately after post-testing in block 1, and block 3 will begin immediately after post-testing in block 2. See Figure below. Of note, turning the stimulator off and on is a typical occurrence in the medical setting. This allows patients to get used to the stimulation and also is necessary to change batteries in the control box. This externalized control box is easily accessible and has simple controls for turning the unit on and off. Post-tests will include the same battery of clinical respiratory assessments and diaphragm EMGs as pre-testing and will take approximately 1 hour to complete. The duration of stimulation varies for each block:

Block 1: ~1 hour of stimulation (no longer than 2 hours*) followed by post-test 1

Block 2: ~ 1 hour of stimulation (no longer than 2 hours*) followed by post-test 2

Block 3: ~ 12 hours of stimulation (no longer than 24 hours*) followed by post-test 3

Figure 3

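### The wavelet interpretation lets a frequency shift between maneuvers, measurable before any stimulation, count as support for a stimulation effect

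*Combined protocol and SAP*

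**What the plan says.** All references are to section 6 (Research Plan) of the combined protocol and SAP unless stated.

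- **Two frequency comparisons.** The wavelet text under Neuromuscular activation outcomes announces "Comparisons of the frequency characteristics of the EMGs recorded during different respiratory maneuvers and longitudinally".
- **What a shift means.** As an example, it says "a shift toward higher frequencies during more forceful maneuvers or over-time would suggest recruitment of larger, more forceful motor units".
- **What that supports.** The following sentence opens "Such changes would support our previous observations" and ends with the proposition "that intramuscular stimulation promotes neural and muscular adaptations".
- **Status.** Under Assessment of neuromuscular activation of the diaphragm, the wavelet measures are one of three families of primary outcomes. The other two are amplitude and timing, and neural respiratory drive.
- **When the data are collected.** Under Pre-stimulation Assessment: "The pre-stimulation assessment will include clinical respiratory tests and recording of diaphragm EMGs". That assessment is done twice before the pacer is turned on ("two sets of tests will be conducted, about 1 hour apart"). Under Post-tests: "Post-tests will include the same battery of clinical respiratory assessments and diaphragm EMGs as pre-testing".
- **Planned test.** Statistical analysis specifies a Mann-Whitney U comparison of EMG and respiratory outcomes before and after the stimulator is activated. It names no frequency summary and no maneuver.

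**The concern.** The word joining the two kinds of shift is an *or*, and the next sentence carries both forward to the stimulation claim. Read as written, a higher frequency during a maximal effort than during tidal breathing is enough to be cited as support for stimulation-induced adaptation. By the plan's own account, that shift is what recruitment of higher-threshold units with force produces. It needs no stimulation.

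The aim of the study is to isolate what pacing itself contributes, and its results are meant to justify and inform a larger trial. The design is a single cohort with no unstimulated group, so no control arm would expose a shift that was present all along. A normal physiological contrast could then be reported, within a primary outcome family, as a sign that pacing works. This does not depend on noise: it would hold with a perfect EMG recording.

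**Working it through.** The plan gives no frequency values, SDs, thresholds, alpha or effect size for this outcome, so there is no stated figure to reproduce. The main check is logical; a simulation then illustrates it.

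**1. Are both maneuvers recorded before stimulation?** The Assessment Overview puts maximal inspiratory pressures in each assessment, concurrent with EMG, together with tidal breathing. Neural respiratory drive, another primary outcome, is tidal EMG divided by maximal EMG and so needs both. The pre-stimulation assessment includes EMG and the respiratory tests. Unless a test is omitted for medical reasons, the maximal-versus-tidal contrast therefore exists at time 0.

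**2. Which contrasts carry information about stimulation?** Let f(m,t) be a frequency summary for maneuver m (T tidal, M maximal) at time t (0 pre-stimulation; k = 1, 2, 3 post-tests).

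- Between maneuvers: B(t) = f(M,t) − f(T,t)
- Over time, same maneuver: D(m,k) = f(m,k) − f(m,0)

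If stimulation does nothing and nothing else changes, f(m,k) equals f(m,0) on average. Then D(m,k) averages 0, while B(k) and B(0) both average δ, the ordinary recruitment step. A positive B shows that δ is positive and nothing more. Only D(m,k), or the change B(k) − B(0) = D(M,k) − D(T,k), can bear on stimulation.

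**3. Illustration with zero stimulation effect.** Inputs from the plan: 5 people completing tests, 10 enrolled, Mann-Whitney U. Inputs assumed: alpha 0.05 two-sided with an upward shift required; normal data with total SD 1; within-person correlation 0.5; δ from 0 to 3 SD; 4,000 runs per setting. Entries are the percentage of simulated studies meeting each criterion.

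| n | δ (SD) | Maximal vs tidal, pre-stimulation only | Same maneuver over time | Either route | Change in B |
|---|---|---|---|---|---|
| 5 | 0 | 0.3 | 0.4 | 0.7 | 1.5 |
| 5 | 0.5 | 4.1 | 0.4 | 4.0 | 1.7 |
| 5 | 1 | 16.9 | 0.4 | 16.8 | 1.5 |
| 5 | 2 | 72.0 | 0.4 | 70.9 | 1.7 |
| 5 | 3 | 96.4 | 0.4 | 97.4 | 1.8 |
| 10 | 0 | 0.4 | 0.4 | 0.9 | 2.2 |
| 10 | 0.5 | 10.1 | 0.4 | 10.7 | 2.2 |
| 10 | 1 | 52.7 | 0.4 | 51.3 | 2.1 |
| 10 | 2 | 99.5 | 0.4 | 99.5 | 2.0 |
| 10 | 3 | 100.0 | 0.4 | 100.0 | 1.8 |

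The either-route column uses the post-test maximal-versus-tidal contrast or the pre-to-post change in the maximal maneuver. It closely tracks the pre-stimulation-only column, so nearly all the false support comes from the maneuver route. The two pre-to-post columns do not depend on δ.

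The 0.4% is low partly because a Mann-Whitney test ignores the positive within-person correlation. The change in B removes the person effect. At n = 5 its rate should be near the exact one-direction size: 4 of C(10,5) = 252 orderings, or 1.6%. The simulated 1.5% to 1.8% agrees.

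**4. Would the planned test make the error?** No. It compares before with after, so a contrast that is equally present at both times would not register. The gap is that the wavelet interpretation is not tied to that test.

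**The case against.** The strongest reply is that this is not a decision rule. The sentence is introduced as an example, says only that a shift would suggest recruitment, and sets no threshold. The comparison that yields results is pre versus post: Statistical analysis says so, the Research AIM in section 4 describes EMG recordings before and after pacing, and the primary outcomes are meant to assess changes associated with stimulation. The conclusions listed under Interpretation and possible outcomes rest on activation and respiratory function, not on frequency differences between maneuvers. All of this stands, and it limits the point to interpretation. It does not remove it, because the plan gives no other account of how a wavelet result bears on stimulation.

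A reader might go further and infer that the over-time comparison is equally unsafe because it is not tied to one maneuver. The documents do not support that. Post-tests repeat the pre-stimulation battery, positions and procedures are standardized, and maximal maneuvers are repeated about 3 to 5 times, so comparing like with like is the natural reading. Voluntary effort can still differ between sessions, which is a reason to show the pressure alongside the frequency.

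A reader might also want maximal efforts matched on pressure. That would condition on an outcome. Inspiratory pressure is the plan's index of diaphragm strength, and the hypothesis is that pacing improves respiratory function. Discarding post-test efforts that exceed the pre-stimulation pressure could remove a real effect and bias the result toward null.

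**Conclusion.** The point holds as a flaw in the stated interpretation of a primary outcome family. A maximal-versus-tidal frequency shift can be seen before stimulation, reflects recruitment with force, and should not be listed as support for a stimulation effect.

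Its practical size is unknown. The 0.7% to 97.4% range at n = 5 (0.9% to 100% at n = 10) is driven by the assumed δ. It also presumes that someone reports the maneuver contrast as a stimulation finding. It is not an error rate of the planned analysis.

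A reader might infer that the study can reach its overall conclusion with no stimulation effect. The documents do not support that reading, because the formal comparison is pre versus post and the overall conclusions do not cite between-maneuver frequency shifts. Correcting the text will not separate stimulation from time or recovery: without an unstimulated comparison, the two pre-stimulation sets give only a short check on drift.

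**What to change.** 1. In the wavelet text under Neuromuscular activation outcomes, delete the reference to more forceful maneuvers from what counts as support for a stimulation effect.
2. Define the wavelet effect as the within-person change from pre-stimulation to each post-test in one named frequency summary for the same maneuver: tidal with tidal, maximal with maximal. State how the two pre-stimulation sets are combined, and analyse the changes as paired data.
3. Keep the pre-stimulation maximal-versus-tidal shift only as a check that the recording detects recruitment.
4. Do not restrict the analysis to pressure-matched efforts. Report the concurrent inspiratory pressure change beside the frequency change, with any pressure-matched comparison as descriptive only.
5. Refer to this definition under Statistical analysis, so that test and interpretation concern the same quantity.

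The cost is a few sentences. EMG and pressure are already recorded together, and no procedure or clinical care changes. One consequence should be stated: with 5 completers and no ties or zero changes, a two-sided signed-rank test cannot go below 2/2^5 = 0.0625 (2/2^10 = 0.002 with 10). The paired result should therefore be presented mainly as individual changes and an estimate with its uncertainty.
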